**Table 3: Comparison IOP Measurements in Clinical routine and ARGOS-SC01\_Follow-up study**

Ophthalmological recommendation for appropriate patient care of glaucoma / glaucoma suspected patients (Leitlinie Nr. 15a  )	Measurements in the ARGOS-SC01_Follow-up study

 
• Tonometry approximately 4 times a year and in case of e.g. deterioration of findings or doubts about compliance, at different times of day
 
• Assessment of the optic nerve and nerve fibrous layer at least once annually
 
• Perimetry at least once a year
 
• Gonioscopy at least at the time of initial diagnosis
 
	
 
• Tonometry with GAT and DCT semi-annual. ARGOS-SC measurements 4 times Daily (as recommended by physicians: morning, noon, afternoon and in the evening)
 
• Fundoscopy semi-annual
 
• Perimetry semi-annual
 
• Gonioscopy semi-annual
 

 Leitlinie Nr. 15a: Primary chronic open angle glaucoma, normal pressure glaucoma and ocular hypertension; Berufsverband der Augenärzte Deutschlands e.V., Deutsche Ophthalmologische Gesellschaft e.V., October 2006

IOP Implandata Ophthalmic Products GmbH	Clinical Investigation Plan ARGOS-SC01_Follow-up	Revision C
		Page 48 of 97

**Patients are therefore not exposed to any significant additional burden or risk beyond the clinical examination that is already regularly required.**

**Data Privacy Risks** – Health data about study patients will be collected and transferred to a state of the art electronic database. The data is stored pseudonymized. The sponsor has no access to personal data.

Patients will be requested to attend visits on a regular basis. Patients will be reminded that their continued participation is voluntary and in their best interest.

### **6.3        Possible Interactions with Concomitant Medical Treatments**

The 12 o'clock quadrant of the eye is occupied because of the pressure-lowering surgical intervention in these patients.

 Implantdata Ophthalmic Products GmbH	Clinical Investigation Plan ARGOS-SC01_Follow-up	Revision C  Page 49 of 97
---	---	---------------------------------

Possible interactions of the ARGOS-SC implant with other devices and/or substances used in treatments of the eye:

- **High energy ultrasound:** Do not use high energy ultrasound in the vicinity of the implant
- **Diathermy:** Do not use diathermy in the vicinity of the implant
- **Therapeutic ionizing radiation:** Do not use therapeutic ionizing radiation in the vicinity of the implant
- **Laser:** Do not expose the implant to direct laser energy impact to avoid damage to the implant's electronic components.
- **Interaction of the device with topically applied ophthalmic medications:** Although the device could theoretically affect effectiveness of the medication, thereby compromising therapeutic success of medication could interfere with functionality of the device, these risks are considered very unlikely. No drug-device interaction was observed either during pre-clinical studies in rabbits [42] or during the ARGOS-02 study with the technical similar eyemate-IO device.

**Interactions with other general medical procedures:**

- **Magnetic Resonance Imaging (MRI):** it is safe to use MRI with the ARGOS-SC implant for MRI field strength of up to 3T (please refer to section 9 in the Implant IFU for details).
- **X-ray:** High energy gamma radiation must not be targeted towards the ARGOS-SC implant.
- **Other devices generating high-frequency electromagnetic fields:** The device meets the current requirements for EC and electronic radiation immunity.

**Interactions with other active implanted medical devices:**

- **Pacemakers:** the ARGOS-SC reader device must not be activated in direct proximity to a pacemaker generator
- **Implantable cardioverter defibrillator (ICD):** the ARGOS-SC reader device must not be activated in direct proximity to an ICD generator.
- **Cochlear Implants:** the ARGOS-SC is contraindicated in patients with cochlear implants
- **Other (head and neck region) nerve stimulators:** the ARGOS-SC is contraindicated in patients with other nerve stimulators

 Implantata Ophthalmic Products GmbH	Clinical Investigation Plan ARGOS-SC01_Follow-up	Revision C  Page 50 of 97
--	---	---------------------------------

#### **6.4 Risk/Benefit Assessment**

The regular follow-up of the ARGOS-SC01 patients represents a low risk compared to the clinical standard of care routine of these glaucoma patients. The benefit to a patient of participating in the ARGOS-SC01\_Follow-up study outweighs the low risks described above. The ARGOS-SC system will help the patients to actively monitor their condition, which will in turn improve their motivation and ultimately compliance. This is particularly important in a disease where the loss of vision normally occurs gradually over long periods of time and is often only recognized in advanced cases. Additionally, it gives the treating ophthalmologists valuable information about the individual disease of a patient and the effectiveness of the medication regimen.

**Consequently, the medical benefits of direct IOP measurement and frequent self-tonometry by patients at home clearly outweigh the identified risks of the regular follow-up of these ARGOS-SC patients and the ophthalmological measurements that are already necessary and that have to be performed during routine ophthalmological visits.**

 Implantdata Ophthalmic Products GmbH	Clinical Investigation Plan ARGOS-SC01_Follow-up	Revision C  Page 51 of 97
---	---	---------------------------------

## 7. OBJECTIVES AND HYPOTHESES OF THE CLINICAL INVESTIGATION

### 7.1 Objectives

The purpose of this study is to evaluate the long-term safety and performance of the ARGOS-SC suprachoroidal pressure sensor in patients with glaucoma who underwent non-penetrating glaucoma surgery.

#### 7.1.1 Primary Objectives

*Performance*

- To evaluate the limits of agreement between measurements with the GAT, DCT and the ARGOS-SC system from month 12 throughout month 36 following implantation.

#### 7.1.2 Secondary Objectives

*Safety*

- To evaluate the safety and tolerability of the ARGOS-SC pressure sensor throughout a follow-up period from month 12 throughout month 36.

*Performance*

- To evaluate the performance of the ARGOS-SC system from month 12 throughout month 36.

### 7.2 Claims and intended performance of the IMD to be verified

This study is designed to show agreement between IOP measurements obtained with the ARGOS-SC device, GAT and DCT at the same time point. Furthermore, it will allow long-term assessment of the implanted ARGOS-SC sensor.

### 7.3 Risks and anticipated adverse device effects to be assessed

Information will be collected on all AEs and ADEs to allow assessment of the long-term safety of implantation and use of the ARGOS-SC sensor in humans who underwent non-penetrating glaucoma surgery. Particular attention will be paid to ophthalmic AEs, for which increased risks are considered possible. However, because these AEs are common in this patient population, an independent assessment of their relationship to the ARGOS-SC sensor implant will not be possible.

 Implantata Ophthalmic Products GmbH	Clinical Investigation Plan ARGOS-SC01_Follow-up	Revision C  Page 52 of 97
--	---	---------------------------------

Possible adverse device effects will be subject to evaluations of the DSMB. Incidence, nature and severity will be compared to literature of standalone NPGS. AEs of particular interest include:

- Perforation/Rupture of the trabeculo-descemet's membrane (TDM)
- Anterior chamber inflammation
- Hypotony (IOP < 5 mmHg for more than one month or hypotony maculopathy (e.g. with signs of maculopathy))
- Shallow anterior chamber
- Suprachoroidal hemorrhage
- Choroidal detachment
- Retinal detachment
- Hyphema
- Iris incarceration in TDM
- Temporary visual impairment as a secondary effect caused by the adverse events described above

Procedures that are anticipated in the general patient population in the follow-up period include:

- 360°-suture removal after canaloplasty
- Nd:YAG membranectomy
- Nd:YAG goniopuncture
- Nd:YAG iridotomy
- Retinal detachment repair
- Transcleral cyclophotocoagulation
- Vitrectomy with epiretinal membrane peeling
- Choroidal drainage
- Anterior chamber infusion with or without recombinant tissue plasminogen activator
- Re-suturing of the scleral flap
- Subconjunctival injection of dexamethasone
- Inserting a therapeutic soft contact-lens

 Implantdata Ophthalmic Products GmbH	Clinical Investigation Plan ARGOS-SC01_Follow-up	Revision C  Page 53 of 97
---	---	---------------------------------

## 8. DESIGN OF THE CLINICAL INVESTIGATION

### 8.1 General Aspects

#### 8.1.1 Description of the type of clinical investigation

This prospective, open-label, single-arm follow-up multicenter clinical investigation will enroll only subjects of the ARGOS-SC01 study with an implanted ARGOS-SC pressure sensor.

Subjects will be followed-up at regular intervals for 2 years (Month 12 – Month 36 following implantation).

To investigate the performance of the device and detect possible safety issues, patients will undergo ophthalmic examinations and be questioned regarding their health by the investigator at every visit.

Additional visits may be held as deemed appropriate by the investigator. The content and reasons for visits will be documented on a separate unscheduled visit CRF.

#### 8.1.2 Description of the measures to be taken to minimize or avoid bias

All eligible patients will be enrolled.

There will be no control group for safety events. Incidence, nature and severity will be compared to literature of standalone NPGS. To allow assessment of performance, measurements of IOP with the ARGOS-SC sensor will be compared to those obtained with the standard GAT method and Pascal DCT at the same time point. To prevent possible influence of prior knowledge of the IOP value obtained with the ARGOS-SC, which is objectively displayed, measurements will always be made first with GAT/DCT. Data on all device deficiencies will be recorded.

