## 4. IDENTIFICATION AND DESCRIPTION OF THE INVESTIGATIONAL DEVICE

### 4.1 Summary description of the investigational device and its intended purpose

The ARGOS-SC system was developed for the wireless, contactless measurement of the hydrostatic pressure of the aqueous humor of the human eye (IOP). It is made up of two components: the ARGOS-SC implant and the external hand-held Mesograph reading device (with the later one already carrying CE mark as an accessory for the eyemate-IO posterior chamber IOP sensor implant). An additional component, the Multiline connector, can be used by the subjects between study visits to upload recorded measurement data from the Mesograph reading device to a secure centralized database that can be accessed by the investigator.

The ARGOS-SC implant is comprised of a micro-electromechanical system (MEMS) application specific integrated circuit (ASIC) bonded to a micro-wire wound coil of gold and encapsulated in a special silicone-rubber material that has been extensively proven to be well tolerated by the eye when silicone intraocular lenses (IOL) were still popular. It is intended to be implanted during otherwise required ocular surgery and to remain in place indefinitely. In the ARGOS-SC01 study, the implant is introduced into suprachoroidal space of the eye during non-penetrating Glaucoma surgery, using the associated surgical access.

Activation of the Mesograph reading device in the near vicinity of the eye establishes an inductive link between the reader and the micro-coil. This induces a slight current in the otherwise electrically passive implant, supplying it with power and permitting data transmission. Pressure-sensor cells and an A/D converter incorporated in the ASIC measure IOP and the digitized data is then transmitted to the reader. Data is stored in non-volatile memory inside the reader device, preventing data loss in case of an error, and can be uploaded to a computer, or to an internet-based database through the Multiline connector.

 Implantdata Ophthalmic Products GmbH	Clinical Investigation Plan ARGOS-SC01_Follow-up	Revision C  Page 23 of 97
---	---	---------------------------------

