### **8.3.11     Performance**

IOP level will be assessed at every follow-up visit in a series of 2 GAT standard measurements followed by 3 consecutive measurements with the ARGOS-SC system and if available, additional 2 DCT measurements followed by 3 consecutive measurements with the ARGOS-SC system.

Patients were given a MESOGRAPH reading device at Visit 01 in order to measure the IOP daily at home. Measurements shall be taken at least 4 times per day (morning, noon, afternoon, evening). The

 IOP Implantata Ophthalmic Products GmbH	Clinical Investigation Plan ARGOS-SC01_Follow-up	Revision C  Page 59 of 97
---	---	---------------------------------

MESOGRAPH reading device will be connected to an external GSM module, which will transfer the measured value directly to a secure database. Investigators can log into the database in order to track the pressure levels of their patients as required. At every follow-up visit, site staff will examine the subject's hand-held reader device and download all readings recorded since the last visit. In addition, they will ask subjects non-leading questions to determine if any device deficiencies occurred since the last visit. All device deficiencies will be recorded on the device deficiency page of the CRF. To ensure accuracy and comparability of the recorded parameters, all responsible site personnel will be thoroughly instructed on the agreed measurement methods.

To access the user acceptance of the general usability of the ARGOS-SC system, physicians and personnel performing the ARGOS-SC system measurements will be asked to complete user acceptance questionnaires. The aim of these questionnaires is to gain more information about the level of user-acceptance of the ARGOS-SC system during IOP measurement. The data collected with these questionnaires is only of exploratory nature and will not be included in the analysis. Results will provide the sponsor with data that could influence future device system improvements.

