### **IOP measurement in the clinic**

IOP measurement will be conducted as a series of 2x GAT (in case of a difference of more than 2mmHg, a third GAT-measurement is required) followed by 3x ARGOS-SC system. When series of measurements are made, GAT must always be used first to avoid potential operator bias. For the ARGOS-SC measurements the patient has to stay in the same position as for the GAT-measurements (chin on chin rest, forehead installed).

Additionally (if available), a series of 2x DCT (in case of a difference of more than 2mmHg, a third DCT-measurement is required) followed by 3x ARGOS-SC will be performed after the series of GAT and ARGOS-SC measurements. For the ARGOS-SC measurements, the patient has to stay in the same position as for the DCT-measurements (chin on chin rest, forehead installed).

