 External eye photography is performed through a slit lamp camera or equivalent. The outer eye shall be photographed in order to document potential changes to the iris or pupil structure.

 Anterior segment OCT is performed to evaluate effects on change in chamber angle after non-penetrating glaucoma surgery and to assess corneal thickness.

 Slit-lamp biomicroscopy is performed through an undilated pupil to assess the following anatomic parameters of the anterior segment: lids, conjunctiva, cornea, anterior chamber, iris, pupil, lens and anterior vitreous body.

 Standard gonioscopy is used to confirm glaucoma classification and to evaluate the presence of iris tumors, foreign bodies, anterior synchiae and to predict the anterior chamber angle. The gonioscopic grading system according to Shaffer is used in this clinical investigation.

 Funduscopy is performed by means of indirect ophthalmoscopy on a slit lamp with the aid of a 90D or "Superfield" or comparable lenses. For this examination the pupil needs to be dilated by the use of mydriatic agents. This method is used to evaluate the following parameters: optic nerve lesions, other posterior pole lesions, vitreous opacities, optic nerve head, fundus lesions, retinal arteries and veins (AV), macular area, fundus periphery, normal and abnormal variations of the fundus.

 Posterior segment OCT is used to assess macular structures and the peripapillary nerve fiber layer thickness (RNFLT) and if possible Minimum rim width at Bruch membrane opening (BMO-MRW).

 The fundus should be photographed in order to document potential changes to the optic nerve (cup/disc ratio) and nerve fiber layer (red-free illumination).

 IOP measurements will be made in series of 2 GAT measurements (in case of a difference of more than 2 mmHg, a third GAT measurement is required) followed by 3 directly consecutive ARGOS-SC system measurements; *if DCT is available*: additionally followed by 2 Pascal DCT measurements (in case of a difference of more than 2 mmHg, a third Pascal DCT measurement is required) and 3 directly consecutive ARGOS-SC system measurements.

For the non-study eye, only GAT and DCT measurements will be performed as described above.

All measurements should be performed directly one after another.

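### DCT is taken after three displayed ARGOS-SC readings of the same eye, so the within-visit order safeguard in protocol 8.1.2 works for GAT but not for DCT

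*Protocol*

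**What the plan says.** Protocol 8.1.2 gives a purpose and a rule in one sentence. The purpose is "To prevent possible influence of prior knowledge of the IOP value obtained with the ARGOS-SC, which is objectively displayed"; the rule is "measurements will always be made first with GAT/DCT". It names both tonometers.

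The operational text sets the order:

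- Protocol 8.3.11: two GAT, three ARGOS-SC, then "if available, additional 2 DCT measurements followed by 3 consecutive measurements with the ARGOS-SC system".
- Protocol 8.3.12.13 (measurement in the clinic): the DCT series "followed by 3x ARGOS-SC will be performed after the series of GAT and ARGOS-SC measurements". Its own order rule names one tonometer only: "When series of measurements are made, GAT must always be used first to avoid potential operator bias".
- Protocol Table 4, footnote 10: after the first three sensor readings the sequence is "additionally followed by 2 Pascal DCT measurements" and three more sensor readings, with no pause between any of them. SAP 3.4, Table 1, footnote 10 repeats this.

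Protocol 11.12 says the study is not masked. Protocol 8.1.3.1 and SAP 4.2.1 name DCT in the primary endpoint, and SAP 8.5.1 applies the GAT analysis to DCT by analogy.

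**The concern.** By its own account, 8.1.2 exists so that whoever takes the tonometry reading does not already know what the sensor shows. For DCT, three sensor values for the same eye have been displayed moments before. Nothing in either document covers the display, keeps the values from the DCT operator, or requires a different person to take the sensor readings.

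If a DCT reading is drawn toward a known sensor value, the paired differences shrink. The limits of agreement narrow and the share within 5 mmHg rises, which favours the device. The report could then present DCT agreement as protected by a measure that did not apply to it.

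**Working it through.** **Order check.** Number the readings as specified, without optional third readings: GAT 1–2, ARGOS-SC 3–5, DCT 6–7, ARGOS-SC 8–10.

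- Sensor readings before the first GAT: 0.
- Sensor readings before the first DCT: 3 of the visit's 6.
- Sensor readings between DCT and its own paired set: 0.

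DCT is thus first within its own series, but not first with respect to knowledge of the sensor value.

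**Possible size.** The plan states no figure to reproduce, so this is an illustration. From the documents: the 5 mmHg band and the 65% criterion (protocol 9.1.4), and limits drawn at ±2 SD (SAP 11.2). Assumed, because the documents do not give them: differences are normal with mean zero; their true SD is 6 mmHg (4 mmHg for contrast); DCT is pulled toward the sensor value by a fraction w of the true difference, with w from 0.1 to 0.3; and the first and second sets of three sensor readings show the same pressure, so a pull toward the first set acts fully on the difference from the second.

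The recorded difference is then (1 − w) × the true difference, and

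share within 5 mmHg = 2Φ(5 / [SD × (1 − w)]) − 1.

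| True SD | w | Recorded SD | 5 / recorded SD | Share within 5 mmHg | ±2 SD limits |
|---|---|---|---|---|---|
| 6 | 0 | 6.0 | 0.833 | 59.5% | ±12.0 |
| 6 | 0.1 | 5.4 | 0.926 | 64.6% | ±10.8 |
| 6 | 0.3 | 4.2 | 1.190 | 76.6% | ±8.4 |
| 4 | 0 | 4.0 | 1.250 | 78.9% | ±8.0 |
| 4 | 0.1 | 3.6 | 1.389 | 83.5% | ±7.2 |
| 4 | 0.3 | 2.8 | 1.786 | 92.6% | ±5.6 |

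**Sensitivity to the zero-bias assumption.** Start from a true share of 60%. With zero bias this needs an SD of 5.94 mmHg, and pulls of 0.1, 0.2 and 0.3 give 65.0%, 70.7% and 77.1%. With a 2 mmHg mean bias the SD that gives 60% is 5.58 mmHg, and the three results are the same to one decimal. The bias assumption is therefore not what drives the illustration; w and the SD are.

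**The case against.** The best defence is that 8.1.2 can be read series by series: tonometry first, then its paired sensor readings. The sequence meets that reading, so a flat charge that 8.1.2 is false would go too far. What stands is that the purpose stated in the same sentence is not achieved for DCT on either reading.

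The size may also be small. Protocol 8.2.2 describes DCT as less open to user error. Protocol 4.6 lets any trained person take the sensor readings, so it is an inference, though a natural one in an unmasked study, that the DCT operator sees them. In the illustration, an SD of 4 mmHg passes 65% with or without a pull, and an SD of 6 mmHg with a 10% pull still falls just short. The SAP performs no tests (8.1.3).

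A reader might infer several stronger things that the documents do not support:

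- *That order is the only bias safeguard.* Protocol 8.3.12.13 also asks sites to keep the number of tonometry operators low. That does not conceal the sensor value, but it is a bias measure.
- *That the operator chooses whether to take a third DCT reading.* The rule is numerical: a third is required when the two differ by more than 2 mmHg.
- *That DCT is half of the primary endpoint.* DCT is done only where available, protocol 8.2.2 justifies GAT as the comparator, and SAP 8.5.1 itemises only the GAT and ARGOS-SC averages before adding DCT by analogy.
- *That GAT and DCT might be pooled.* The SAP already gives them separate tables (2.1.1 and 2.1.2) and separate figures (1–10 and 11–20).

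**Conclusion.** The point holds in limited form. The order safeguard that 8.1.2 states for both tonometers works within the visit for GAT and not for DCT. This follows from the specified sequence and needs no numerical assumption. The direction of any resulting bias favours the device. Its size is unknown: 59.5% becoming 64.6–76.6% shows only what a 10–30% pull would do at an SD of 6 mmHg under the stated model, and the documents supply neither value. It does not show that DCT agreement is in fact inflated, or that the 65% criterion would be wrongly met.

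The words within the visit matter. Protocol 8.3.11 and 8.3.12.13 let investigators view home readings in the database, so even GAT is not fully shielded from earlier sensor values by the order rule. SAP section 9 says self-measurements were not recorded, so how far that route was open is unclear.

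**What to change.** **Visits still to come.** Keep the sequence. Require that the first three ARGOS-SC values be withheld from the tonometry operator until the DCT values are recorded, either by covering the display or by having another trained person take the readings. The values can be retrieved later, since "Data is stored in non-volatile memory inside the reader device" (protocol 4.1). Protocol 8.3.12.13 has staff delete reader data at each visit, so the instruction must say that the values are saved before deletion. This changes a procedure, so it needs a formal amendment with the approvals in protocol 11.4 and 11.8. A minor cost is that a failed sensor reading may be noticed later.

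**Visits already done.** Correct 8.1.2 to say that the within-visit order safeguard applies to GAT only. Add a sentence to SAP 8.5.1 stating that DCT was taken after ARGOS-SC values had been displayed, and that DCT agreement is therefore supportive and unmasked. SAP section 2 places finalisation before database lock, so the sentence fits that timetable. It costs one sentence in each document and no change to the analysis or sample size.
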